11.0 Statistical Consideration

11.1 Sample Size Justification

Primary endpoint is the percent change in NT-proBNP at 6 months from baseline, which is defined as the absolute change divided by the baseline value multiplied by 100. A total sample size of 60 (30 in each group) will be enrolled, accounting for ~13% drop out rate to have 52 subjects with a primary endpoint. Enrolled participants who were dropped out of study will be replaced with additional participants if more than 13% participants were dropped out of the study. A sample size of 30 in each group produces a 95% confidence interval equal to the sample mean change in NT-proBNP plus or minus 10 when the estimated standard deviation is 25, accounting for ~13% drop out rate. There is no preliminary data and there are no similar studies to obtain preliminary estimates for the percent change in NT-proBNP in any of 2 arms.

Therefore, the sample size calculation was performed based on an effect size of 0.8, which is considered as large. Group sample sizes of 30 and 30 achieve 80% power to detect a standard effect size of 0.8 (for example, mean percent difference of 20 when the standard deviation of 25) with a significance level (alpha) of 0.05 using a two-sided two-sample t-test, accounting for ~13% drop out rate. PASS 2005 (Hintze, J. (2004). NCSS and PASS. Number Cruncher Statistical Systems. Kaysville, Utah.

www.ncss.com) was used for the sample size calculation. The caveat is that if the true effect size is smaller than the effect used in power calculation then the calculated sample size will not be enough to achieve 80% power. In case the study turns to be not significant but promising in this setting, these data can be used as preliminary estimates to design a bigger trial.

After enrolling 60 subjects, we evaluated the observed drop-out rate. Three subjects were not randomized yet. Six-month follow-up was not reached for 13 subjects. Sixteen subjects were dropped out of the study (withdrawn prior to randomization (n=6), randomized but withdrawn prior to receiving study treatment (n=4), and randomized, treated, but withdrawn prior to 6-month follow-up (n=6)). Drop-out rate among those who were enrolled, excluding those not reaching 6-month follow-up and those not randomized yet, is 36% (16/44). Since the drop-out rate is higher than 13%, we will enroll additional subjects to replace those who dropped out of the study.

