Among those who received the study drug, 28 subjects have completed 6-month follow-up; 13 subjects were not reached 6-month follow-up yet; 6 subjects were withdrawn prior to 6-month follow-up. 6-month follow-up completion rate among those who received the study drug and reached 6-month follow-up visit is 82% (28/34). At this rate, we expect that 10 of 13 not reaching 6-month will complete 6-month follow-up. To have 52 subjects with a primary endpoint, we still need 14 (i.e., 52-38) additional subjects with a primary endpoint.

Applying the drop-out rate of 36%, we may need to enroll 19 additional subjects in addition to 3 subjects who were not randomized yet. As we enroll additional subjects in the study, we will monitor the number of subjects who complete 6-month follow-up with a primary endpoint. Our goal is to have 52 subjects with a primary endpoint. We will stop enrolling additional subjects once the number of subjects who complete 6-month follow-up with a primary endpoint reaches 52.

If needed, we will evaluate the observed drop-out rate and re-estimate the number of

additional subjects to enroll to have 52 subjects with a primary endpoint after enrolling 19 additional subjects,

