11.2 Statistical Analysis Plan

We will analyze two analysis sets, including modified intention-to-treat and per protocol analysis sets. Modified intention-to-treat analysis set will include all patients who were randomized and started a study treatment, regardless of whether they received treatment as planned. Per protocol analysis set will include all patients who received treatment as planned.

Patient baseline characteristics and outcome variables (primary endpoint and secondary endpoints (absolute changes and percent changes for continuous endpoints)) will be summarized by study arm, using mean (standard deviation (SD)) or median (inter quartile range (IQR)) for continuous variables and frequency (%) for categorical variables. Repeatedly measured variables will be summarized using descriptive statistics by study arm and by time point (baseline, 3 months, and 6 months). The mean percent

change in NT-proBNP at 6 months from baseline will be estimated in each arm along with the standard deviation. The mean percent change in NT-proBNP will be compared between 2 arms by two-sample t-test. Linear regression model will be used to compare the 2 arms in the mean percent change, adjusting for stratification factors. Those without 3-months or 6-months NT-proBNP may be imputed, using last observation carried forward method or other methods.

Compliance is defined as the total number of medications taken divided by the total number of medications provided during 6 month treatment period. The proportion of patients maintaining at least 70% compliance will be estimated in each arm. Proportion of patients experiencing each type of side effects will be estimated in each arm along with 95% confidence interval (CI). The change from baseline to 3 months and the change from baseline to 6 months in variables described in secondary objectives will be compared within each arm by paired t-test or Wilcoxon signed-rank test for continuous variables and Mantel-Haenszel test for categorical variables. Generalized linear mixed effects models will be used to compare two arms in repeatedly measured outcomes over time. P-values less than 0.05 will indicate statistical significances. SAS 9.4 (Cary, NC) and other relevant software will be used for statistical analysis.

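### Section 11.2 names only an optional LOCF for missing NT-proBNP and does not say which analysis set, test or missing-data rule is primary

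*Combined protocol and SAP*

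**What the plan says.** The missing-data rule for the primary endpoint is one sentence in section 11.2: "Those without 3-months or 6-months NT-proBNP may be imputed, using last observation carried forward method or other methods". No other section fixes a method.

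The same section leaves related choices open:

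- **Analysis sets.** "We will analyze two analysis sets, including modified intention-to-treat and per protocol analysis sets". Neither is called primary. The first set keeps treated withdrawals by definition: "Modified intention-to-treat analysis set will include all patients who were randomized and started a study treatment, regardless of whether they received treatment as planned".
- **Tests.** A two-sample t-test on mean percent change is listed, and then: "Linear regression model will be used to compare the 2 arms in the mean percent change, adjusting for stratification factors". The two are not ranked, and neither is tied to observed or imputed values.
- **Mixed model.** "Generalized linear mixed effects models will be used to compare two arms in repeatedly measured outcomes over time". It is given no role as the primary test or as the way to handle missing NT-proBNP.

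Section 11.1 protects the number of completers: "We will stop enrolling additional subjects once the number of subjects who complete 6-month follow-up with a primary endpoint reaches 52". It does not say how treated patients who left early enter the comparison. NT-proBNP is scheduled at baseline, 3 and 6 months (sections 8.9 and 8.13).

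**The concern.** The modified intention-to-treat set contains patients with no 6-month value, so a comparison in that set needs a rule for them. The only method named is LOCF, and it is optional.

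For a treated patient with no sample after baseline, LOCF records exactly 0% change. For one who leaves after month 3, it records whatever change had occurred by then. Neither value is the 6-month outcome. If the effect is still developing, LOCF pulls the estimate towards zero, even when drop-out is random and equal in the arms.

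Two things are at stake. The primary objective (section 2.0) is to estimate the change in each arm as well as to compare the arms, and section 11.1 says the results may inform a larger trial, so a shrunken estimate would carry forward. Also, an open choice between methods after the data are seen leaves the test without a single defined error rate.

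**Working it through.** **Inputs from section 11.1.** Completed 28; treated and withdrawn 6; treated and still in follow-up 13; target 52 completers; difference 20, SD 25, two-sided alpha 0.05.

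**The plan's own figures.**
- Completion: 28/34 = 82.4%, as stated.
- Count: 28 completed + 16 dropped out + 13 in follow-up + 3 not randomized = 60.
- Power of the t-test with 26 per arm at d = 20/25 = 0.8: 80.7% (noncentral t), against the stated 80%.

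**How many values are missing.**
- 6/34 = 17.6%, exact 95% CI 6.8-34.5%.
- Of all treated at that count: 28 + 13 + 6 = 47, and 6/47 = 12.8%, with 13 unresolved.
- At 52 completers: 52/(28/34) = 63.1 treated, so 63.1 - 52 = 11.1 without a 6-month value. The plan's own projection (38 of 47 completing) gives about 12 of 64.

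**LOCF under equal random drop-out.** Let m = 6/34, true effect -20, control mean change 0 (assumed). If a share s of drop-outs has a month-3 sample carrying a fraction f of the effect, the expected LOCF contrast is -20 × [(1 - m) + m × s × f].

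| Month-3 assumption | Calculation | Contrast |
|---|---|---|
| No month-3 sample (all set to 0%) | -20 × 0.824 | -16.5 |
| Half carry half the effect | -16.47 - 0.176 × 0.5 × 10 | -17.4 |
| All carry half the effect | -16.47 - 0.176 × 10 | -18.2 (simulated -18.3) |
| All carry the full effect | -20 × 1 | -20.0 |

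Power for LOCF with 63 treated:
- All set to 0%: the pooled SD falls to 23.3 because imputed zeros have no spread; d = 16.5/23.3 = 0.71, power 79%.
- All carry half the effect: SD 25.1, d = 0.73, power 81%.
- All carry the full effect: d = 0.80, power 88%.

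**Simulation.** 20,000 trials per scenario, 32 and 31 treated, SD 25 at both visits, assumed correlation of 0.5 between visits.
- True effect -20, equal random drop-out: completers and a two-visit likelihood model each give -20.0 to -20.1, with power of about 80-81%.
- No effect and no drift: type I error is about 5% for each method alone. If a significant result from either completers or LOCF may be reported, it is 5.2-6.4%. The upper end arises when half the drop-outs carry a month-3 value.

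**The case against.** **The t-test is powered on completers.** Section 11.1 sizes the t-test for 52 patients with the endpoint and enrols until they exist. The natural reading is an observed-data comparison with imputation as a supplement. Such a comparison is unbiased under random drop-out and keeps its planned power. This stands as a plausible intention, but section 11.2 does not state it, and the analysis set it defines includes the patients that this reading leaves out.

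**A mixed model is already planned.** True, and it may cover NT-proBNP, but it is not named as primary. For patients with no month-3 sample it gains nothing over completers, and the documents do not say how many of the 6 had one. Its advantage arises when drop-out depends on month-3 values.

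**LOCF need not shrink the effect.** Correct. If every drop-out has a month-3 sample and the effect is complete by then, LOCF is unbiased with about 88% power. The documents give no time course for NT-proBNP, so this case cannot be excluded; nor can the plan rely on it.

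**The 18% is soft.** It counts withdrawals, not absent assays. Its denominator leaves out 13 patients still in follow-up, so early leavers count at once and completers only at 6 months. The range should travel with it.

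**Readings that go further than the documents:**
- *Serious type I error inflation.* With an assumed 20-point rise in both arms and drop-out of 30% against 6%, LOCF error reaches 9-13%, or 12-15% if either method may be reported. The documents show neither drift nor unequal drop-out. If drop-out is equal, a gap of 7 or more patients has about a 3% chance.
- *Bias in favour of the drug.* Reversing the split reverses the sign, and section 11.3 reports similar adverse event incidence across groups in earlier trials.
- *A need to change section 10 or the 52-completer rule.* Section 6.3.2 already separates stopping the drug from leaving the study. At the observed rate, draws after drug discontinuation could recover at most about (63.1 - 34) × 6/34 = 5 values. If the effect is wholly lost off drug, adding 5 such draws lowers power from 80.7% to about 77%. The cap of 79 leaves little room to tighten the rule: 47 + 22 × 47/57 = 65.1 treated, × 28/34 = 53.6 completers, about two to spare.

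**Conclusion.** The concern holds as a cheap improvement. The primary analysis is not fixed for roughly one in six treated patients (17.6%, 95% CI 7-35%, with withdrawal as the proxy for a missing value), and the only named method is weaker than one the plan already has the data and model class to run.

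Under equal random drop-out, LOCF loses 1.8 to 3.5 of 20 points, except where month-3 values already hold the full effect. These figures rest on the plan's difference and SD and on assumed month-3 values. Power under LOCF is 79-88% across these cases, against about 80% for completers or the likelihood model, so this is not a power failure. The cost of the open choice between completers and LOCF is small without drift: 5.2-6.4% instead of 5%. No direction of bias is claimed.

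**What to change.** Before unblinding, amend section 11.2 as follows:

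1. Delete LOCF and the open-ended alternative.
2. Name one primary analysis in the modified intention-to-treat set: a likelihood-based repeated-measures model of percent change in NT-proBNP at 3 and 6 months, with arm by time, stratification factors and baseline. The 6-month contrast is the test.
3. Add one delta-adjusted multiple-imputation sensitivity analysis that includes treated patients with no post-baseline sample. Impute by arm from baseline, stratification factors and month 3 where present. Add a delta from 0 to +20 points (the planned difference) to imputed 6-month values in the drug arm, then in the placebo arm. At 17.6% missing, the largest delta moves the contrast by 20 × 0.176 = 3.5 points.
4. Show the completer t-test as supporting.

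The endpoint, visit schedule, section 10 and the 52-completer rule stay as they are. The cost is one text amendment and a little more analysis work, with no new visits or samples. Section 1.0 estimates completion at the end of August 2025 and the documents do not show the current status, so the change carries weight only if it is dated before unblinding.

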2. The change in CVHD score from baseline at 3 and 6 months , change (significant change or non-significant change) in global longitudinal myocardial strain assessment of the left and right ventricle from baseline at 3 and 6 months, change (normal or abnormal) in TAPSE from baseline at 3 and 6 months
3. The change in plasma 5-HIAA levels from baseline at 3 and 6 months
4. The change in high sensitivity troponin T from baseline at 3 and 6 months
5. The change in quality of life questionnaire (using MD Anderson Symptom Inventory (MDASI)) from baseline at 3 and 6 months
6. The proportion of patients maintaining at least 70% compliance

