6.3.2 Dose Adjustments for adverse events related to the study drug

Adverse Events will be graded as follows (NCI CTCAE version 5.0)

Grade 1 No change in dose
Grade 2 Hold until ≤Grade 1. Resume at same dose level.
Grade 3 Hold until ≤Grade 1. Resume at 1 dose level lower (250 mg tid).
Grade 4 Hold and contact the Primary Investigator

Dose can also be adjusted or discontinued per PI's discretion for patients' safety.

*Patients unable to tolerate 250 mg tid should be discontinued from telotristat ethyl. **Constipation and abdominal pain dose adjustment is different (see below)

6.3.3 Recommended management for the following AEs:**6.3.3.1** Nausea and/or vomiting: treatment with antiemetics**6.3.3.2** Diarrhea: treat underlying cause and/or with antidiarrheal**6.3.3.3** Gastrointestinal toxicity**6.3.3.3.1** Monitor concomitant medication usage**6.3.3.3.2** Constipation (Grade 1 and above): initiate treatment as clinically indicated; examples of therapies include: laxatives, enemas, suppositories, psyllium hydration, over-the-counter (OTC) agents**6.3.3.3.3** Abdominal pain (Grade 1 and above): initiate treatment as clinically indicated; examples of therapies) include: analgesics, anti-gas/bloating agents**6.3.3.3.4** Hold telotristat ethyl for Grade 2 constipation or abdominal pain until \leq Grade 1.**6.3.3.3.5** Discontinue telotristat ethyl for Grade 3 constipation or abdominal pain*(please note this is different than above table)**6.3.3.4** Suicidal ideation: discontinue telotristat ethyl**6.4 Treatment Compliance**

Patients will be asked to bring their unused or unopened bottles of telotristat ethyl to each visit. Patients will be allowed to ship their unused and/or unopened bottles of telotristat ethyl back to PI at MDAnderson if traveling is impossible/restricted. At each visit study site personnel will count returned tablets and reconcile the counts against planned number of doses for that interval. All dosages prescribed and dispensed to the patient, dose modification(s), and missed dose(s), including planned dose interruptions during the study must be recorded. Site personnel are to clarify any discrepancy and record this information.

Patients must maintain at least 70% compliance at clinical visits (3 month interval including allowed window; see section 8 for details) in dosing to be deemed as compliant.

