8.0 Evaluation during Study

- 8.1 Complete history and physical examination done at 3 and 6 months as part of clinical follow-up. (telemedicine technology and language assistant may be used)
**A window of 3 weeks before or after for these visits will be acceptable to accommodate for patient convenience.
- 8.2 CBC with differential, Liver panel (to include AST, ALT, bilirubin, albumin), basic metabolic panel (Sodium, potassium, bicarbonate, chloride, BUN, creatinine, glucose) done at 3 and 6 month (**-asterisk- labs and tests maybe done 3 weeks prior or up to 3 weeks after clinical follow-up date)
- 8.3 ECG done at 3 and 6 months within 6 weeks of clinical visit**
- 8.4 Pregnancy test for females of childbearing age within one week
- 8.5 MDASI done at 3 and 6 months (telemedicine technology and language assistant may be used;can be done within 6 weeks of clinical follow-up)
- 8.6 Echocardiography with a 2D transthoracic echocardiography (2D TTE), 3-dimensional echocardiography (3D TTE), and myocardial strain of the left and right ventricle to be done at 3 and 6 months for those patients with carcinoid heart disease and with carcinoid syndrome and high suspicion of carcinoid heart disease (CHD group), such as those with clinical features or increased NT-proBNP (> 260) mg/ml and/or 5-HIAA levels (24 hr urine 5-HIAA > 100 mg). (**- asterisk- labs and tests maybe done 3 weeks prior or up to 3 weeks after clinical follow-up date
- 8.7 Echocardiography will be done at 6 months in patients with carcinoid syndrome (CS group) who do not have high suspicion for carcinoid heart disease

8.8 Plasma 5-HIAA collection at 3 and 6 months (**-asterisk- labs and tests maybe done 3 weeks prior or up to 3 weeks after clinical follow-up date) (it will be kept frozen in Cryogene lab and will be transferred to Frontage Lab for analysis. More information is included in the lab manual.)

8.9 Cardiac biomarkers to include: N-terminal pro B-type natriuretic peptide (NT-proBNP) and high sensitivity troponin T (HS-troponin T) at 3 and 6 months (**-asterisk- labs and tests maybe done 3 weeks prior or up to 3 weeks after clinical baseline/follow-up date)

8.10 6 minute walk test (6MWT) where distance is recorded in meters at 3 and 6 months (**-asterisk- labs and tests maybe done 3 weeks prior or up to 3 weeks after clinical follow-up date)

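### The 70% compliance cut-off is applied per 3-month interval in Section 6.4 but pooled over 6 months in Section 11.2, and the supply-based denominator in 11.2 can mark down adherent patients (minor)

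*Combined protocol and SAP*

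**What the plan says.** Section 2.0 lists secondary endpoint 6 as "The proportion of patients maintaining at least 70% compliance", with no numerator, denominator or period.

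Section 6.4 (Treatment Compliance) has site staff count returned tablets at each visit and "reconcile the counts against planned number of doses for that interval". It continues: "Patients must maintain at least 70% compliance at clinical visits", with the period given in brackets as "3 month interval including allowed window; see section 8 for details". Section 8.1 states that a "window of 3 weeks before or after for these visits will be acceptable".

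Section 11.2 gives its own definition: "Compliance is defined as the total number of medications taken divided by the total number of medications provided during 6 month treatment period". The next sentence reads: "The proportion of patients maintaining at least 70% compliance will be estimated in each arm".

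Doses can change during the trial. Section 6.3.2 reduces the dose to 250 mg tid after most Grade 3 events, following a hold. Section 6.3.1 allows interruptions of up to 3 weeks. Section 6.4 requires these to be recorded, but neither section says how they enter the compliance ratio.

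**The concern.** One threshold appears with two time bases and apparently two reference quantities. Section 6.4 looks at each visit interval against the plan; Section 11.2 looks at the whole 6 months against supply. A patient with uneven adherence can be compliant under one and not under the other, and no sentence says how the two relate.

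The denominator in 11.2 is a separate problem. Supply is not the same as what the patient was told to take. Stock may be dispensed to cover the visit window, or may already be in the patient's hands when the dose is halved. If it stays in the denominator, following the protocol counts as non-adherence.

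At stake is whether endpoint 6 can be reproduced and whether it measures adherence. If it is left open, the choice could be made after the data are seen.

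**Working it through.** The plan gives no computed figure to reproduce; 70% is a chosen cut-off. The check applies both rules to hypothetical patients.

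**Inputs.** Visits at weeks 12 and 24 (Section 8.14), so two intervals of 84 days. A 3-week visit window (Section 8.1). Two 250 mg tablets tid, i.e. 6 tablets a day (Section 6.2.3). That section also describes the dose as a single 500 mg tablet, but Section 4.6.2 lists only 250 mg tablets as supplied. Reduced dose: 3 tablets a day. No dispensing quantities are given, so every supply figure below is an assumption.

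**1. Time base (no dose change, supply equal to schedule).** Pooled score = (w1 × c1 + w2 × c2) / 24, where w is weeks and c is compliance in each interval.

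| Weeks | Compliance | Pooled | 6.4 | 11.2 |
|---|---|---|---|---|
| 12 / 12 | 95%, 50% | (11.4 + 6.0)/24 = 72.5% | fails | passes |
| 15 / 9 | 95%, 50% | (14.25 + 4.5)/24 = 78.1% | fails | passes |
| 9 / 15 | 95%, 50% | (8.55 + 7.5)/24 = 66.9% | fails | fails |

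After a perfect first interval, the lowest second-interval compliance that still passes 11.2 is (0.7 × 24 − w1)/w2:
- 12/12 weeks: (16.8 − 12)/12 = 40%
- 15/9 weeks: (16.8 − 15)/9 = 20%
- 9/15 weeks: (16.8 − 9)/15 = 52%

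On a common denominator the pooled score is a weighted average of the two intervals, so a patient who passes both always passes 11.2.

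**2. Surplus supply (assumed k extra days per 84-day interval).** A patient who takes 80% of planned doses in both intervals passes 6.4, reading planned doses as its denominator. Under 11.2 the score is 0.80 × 84/(84 + k):
- k = 0: 80.0%
- k = 7: 73.8%
- k = 14: 68.6%, fails
- k = 21: 64.0%, fails

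The adherence needed to reach 70% of supply rises from 70% at k = 0 to 0.7 × 105/84 = 87.5% at k = 21. With surplus, 11.2 becomes the stricter rule.

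**3. Dose reduction (assumed after day 28, no hold, every prescribed tablet taken).** Tablets taken = 6 × 28 + 3 × 140 = 588. Under 11.2:
- Full-dose supply counted for 24 weeks: 588/(6 × 168) = 588/1008 = 58%
- Supply cut at week 12: 588/(6 × 84 + 3 × 84) = 588/756 = 78%
- Stock exchanged at the reduction: 588/588 = 100%
- Doses counted instead of tablets: 504/504 = 100%

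A hold before the reduction lowers the first figure further. With an assumed 7-day hold, taken = 168 + 3 × 133 = 567, and 567/1008 = 56%.

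Section 6.4 shares this weakness if the plan is not reset: (168 + 168)/504 = 66.7% in the first interval and 252/504 = 50% in the second. If it is reset, both are 100%.

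**4. A single 21-day hold, nothing else missed.** 147/168 = 87.5% pooled and 63/84 = 75% in one interval. Both rules are passed.

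**The case against.** The strongest reply is that the two sections do different jobs. Section 11.2 is the analysis plan. It defines compliance and in its next sentence repeats the wording of endpoint 6, so it governs that endpoint. Section 6.4 sits in the treatment plan and says what patients must do, and Section 10.2 makes noncompliance a ground for removal. Most of this stands. A reader might infer that the sections are flatly incompatible, or that nothing indicates which rule applies; the text does not support that. What remains is that no sentence states the division of roles. Section 10.2 does not mention 70%, and the endpoint's notion of maintaining 70% also echoes 6.4.

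Second, 6.4 writes no ratio. Planned doses appear in its tablet-reconciliation sentence, not in its 70% sentence. Reading them as its denominator is the natural inference, not an established fact. The difference in time base does not depend on it.

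Third, the two rules agree when adherence is even and supply equals schedule, and the dose-change results depend on dispensing rules the plan does not give. This also stands. It is tempting to work out the latest day on which a reduction would push a patient below 70%. Such a cut-off would be falsely precise: it needs an assumed dispensing rule and an assumed length for the hold that Section 6.3.2 requires before a Grade 3 reduction.

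**Conclusion.** The point holds as a minor one, best labelled a cheap improvement. The difference in time base is explicit and can reverse a patient's classification (72.5% pooled against 50% in one interval). The supply-based denominator is a stated choice that can misclassify adherent patients. The 58% example assumes that tablets are counted, that 24 weeks of full-dose stock is counted, and that there is no hold; the range across unstated rules is 58% to 100%.

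The number of patients affected cannot be sized. No reduction rate is given, Grade 2 events resume at the same dose, and Grade 3 constipation or abdominal pain leads to discontinuation, not reduction.

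A reader might infer that the per-protocol set or the primary comparison is affected. The documents do not support this. Section 11.2 defines the per-protocol set by treatment received as planned and does not tie it to 70%, and endpoint 6 is only estimated in each arm. Nor is 11.2 always the more lenient rule: that holds on a common denominator and can reverse when surplus is dispensed.

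**What to change.** - In Section 11.2, replace the supply denominator with tablets prescribed under the regimen in force, with protocol-directed holds and reductions removed. Use the same ratio in Section 6.4.
- State that endpoint 6 uses the pooled 6-month value and that the 3-month 70% check in 6.4 is the visit-level conduct rule. Report the proportion reaching 70% in each interval alongside. Making the per-interval rule the endpoint itself would be a preference, not a correction.
- Report dose intensity (tablets taken / full-dose tablets) as well, because the new ratio no longer reflects reduced exposure. The day-28 patient would then show 100% compliance and 588/1008 = 58% dose intensity.

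No new data are needed, since Section 6.4 already requires: "All dosages prescribed and dispensed to the patient, dose modification(s), and missed dose(s), including planned dose interruptions during the study must be recorded". The cost is a short amendment and two extra descriptive summaries. It does change the denominator of a secondary endpoint after 60 patients were enrolled and 28 had completed 6-month follow-up (Section 11.1), so it should be dated and made before unblinding.

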4.0 Background and Drug Information

4.1 Background

Telotristat etiprate is the United States Adopted Name (USAN) for the hippurate salt of telotristat ethyl, the ethyl ester prodrug of LP-778902. In vivo, telotristat etiprate dissociates to form telotristat ethyl which is rapidly converted through the activity of carboxylesterase 1 and 2 to its active metabolite LP-778902. Telotristat ethyl (XERMELO) is a novel, oral, small-molecule tryptophan hydroxylase (TPH) inhibitor that has a high molecular weight and acidic moieties, which inhibits it from crossing the blood-brain barrier. Telotristat ethyl has been shown to lower serotonin (5-HT) levels in the system by inhibiting TPH. Through inhibition of TPH, Telotristat ethyl reduces the production of peripheral 5-HT and the frequency of CS diarrhea and has been FDA approved for the treatment of carcinoid syndrome diarrhea. Two studies in patients with carcinoid syndrome suggested that telotristat etiprate, the hippurate salt of telotristat ethyl, reduced bowel movement (BM) frequency and decreased urinary 5-HIAA without overt CNS adverse effects (27,28). Although the name “telotristat etiprate” was previously granted by the United States Adopted Names Council and has been used in the literature, recent guidance from the US Food and Drug Administration recommends using the name of the neutral form (telotristat ethyl) rather than the name of the salt for drug products.

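### Section 11.2 lets any tested secondary result with p<0.05 be called statistically significant, so a chance finding among the seven non-5-HIAA outcomes has roughly a 23–30% probability

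*Combined protocol and SAP*

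**What the plan says.** Section 2.0 names one primary endpoint, the percent change in NT-proBNP at 6 months. Its secondary endpoints include eight measured outcomes: 6-minute walk, CVHD score, left and right ventricular strain, TAPSE, plasma 5-HIAA, hs-troponin T and MDASI. Each is listed at two visits, for example "The change in high sensitivity troponin T from baseline at 3 and 6 months". Compliance is a further secondary endpoint.

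Section 11.2 plans two kinds of secondary test. Changes to 3 and to 6 months are tested within each arm, by paired or signed-rank tests for continuous variables and a Mantel-Haenszel test for categorical ones. For the arms, "Generalized linear mixed effects models will be used to compare two arms in repeatedly measured outcomes over time". Two analysis sets are planned, modified intention-to-treat and per protocol. The section ends with "P-values less than 0.05 will indicate statistical significances". Compliance and side effects are estimated by arm, with no test described.

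The documents contain no multiplicity adjustment, no testing order, and no statement that secondary results are exploratory or their p-values nominal.

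**The concern.** The closing rule is not a gap in detail. It is a positive statement that gives the same standing to the primary result and to any secondary p-value below 0.05. With several outcomes tested at 5% each, the chance that at least one crosses the line by luck is well above 5%.

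Two features make this matter here. First, the primary is powered for a large effect only ("Group sample sizes of 30 and 30 achieve 80% power to detect a standard effect size of 0.8"), so a non-significant NT-proBNP result is realistic even if the drug works moderately. Second, section 4.1 reports earlier studies in which the drug "decreased urinary 5-HIAA without overt CNS adverse effects". A significant 5-HIAA result is therefore plausible whatever happens to the heart, and nothing in the plan separates such a pharmacodynamic result from evidence of cardiac benefit. A negative primary beside one or two significant secondaries is a foreseeable outcome, and the plan does not say how it should be read.

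**Working it through.** **1. The plan's own figure (section 11.1).** The inputs are "mean percent difference of 20 when the standard deviation of 25", so d = 20/25 = 0.8, tested "with a significance level (alpha) of 0.05 using a two-sided two-sample t-test", and "accounting for ~13% drop out rate to have 52 subjects with a primary endpoint", so 26 per arm.
- Noncentral t power at 26 per arm, d = 0.8: 80.7%. Enrolment: 52/(1 − 0.13) = 59.8, rounded up to 60. The design reproduces.
- The same formula gives 42% power at d = 0.5 and 29% at d = 0.4.

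The plan states no error rate for the secondary family, so there is nothing to reproduce there.

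**2. Number of tests.**
- Eight measured outcomes less 5-HIAA leave seven: walk test, CVHD score, left strain, right strain, TAPSE, hs-troponin T and MDASI.
- Section 11.2 does not say whether the mixed models yield one between-arm test per outcome or one per visit. One each gives 7 tests.
- If 3 months is tested too, sections 8.6, 8.7 and 8.13 matter: 3-month echocardiography is scheduled only for the CHD group. CVHD score, both strains and TAPSE are echo measures, so I add 3-month tests only for the three non-echo outcomes: 7 + 3 = 10.

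**3. Chance of at least one p<0.05 with no true effect.** For k independent tests it is 1 − 0.95^k:
- k = 7: 1 − 0.698 = 30.2%
- k = 10: 1 − 0.599 = 40.1%, an upper reference only, because two visits of one outcome are correlated.

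For correlated tests I simulated two-sided z-tests (400,000 draws, rejection at |z| > 1.96). Outcomes at the same visit have correlation r, visits of the same outcome have correlation v, and different outcomes at different visits have r × v. The documents give neither r nor v; both are assumptions.

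| r between outcomes | 7 tests | 10 tests, v = 0.5 | 10 tests, v = 0.7 |
|---|---|---|---|
| 0 | 30.2% | 38.7% | 37.2% |
| 0.3 | 27.2% | 35.6% | 34.1% |
| 0.5 | 23.0% | 31.1% | 29.4% |
| 0.8 | 14.9% | 21.6% | 20.2% |

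If 5-HIAA were also unaffected, eight tests would give 34%, 30%, 25% and 16% down the same rows.

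**4. Within-arm tests.** Section 11.2 allows up to 8 outcomes × 2 visits × 2 arms = 32. Take the same ten readings in each arm, v = 0.5 and no true change over time. The chance of at least one p<0.05 in either arm is then 1 − (1 − p)²: with p = 0.387 (r = 0), 1 − 0.613² = 62%; with p = 0.311 (r = 0.5), 1 − 0.689² = 53%. These tests measure change over time, so disease course alone can make them significant in either arm.

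Per-protocol repeats are not counted in any of these figures.

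**The case against.** The best defence is that the plan already ranks its questions. There is one primary endpoint. Only the primary objective in section 2.0 speaks of comparing the arms; the secondary change objectives are to evaluate change within each arm. Section 11.1 also foresees a non-significant but promising result and would use the data to design a larger trial. In a small biomarker study, unadjusted secondary p-values are common.

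Much of this stands, and it limits the point. It does not remove it: section 11.2 does plan between-arm secondary tests, and its significance rule covers them without qualification. The sentence in section 11.1 concerns reuse of the data, not what may be called significant.

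A reader might also infer more than the documents support:
- *That the primary result is compromised.* It is not. Secondary testing leaves the 5% error rate of one pre-named primary test unchanged.
- *That about half of null trials would show a significant secondary.* Sixteen independent between-arm tests would give 56%. But section 11.2 does not specify a between-arm test at each visit, two visits of the same outcome in the same patients are not independent, 3-month echo covers a subset, and 5-HIAA is not a plausible null.
- *That every secondary comparison is affected.* Compliance and side effects are only estimated.
- *That a negative trial will be presented as positive.* Nothing in the documents says so. The plan merely fails to rule it out.

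**Conclusion.** The concern holds for the secondary outcomes that are tested. With no true effect on the seven outcomes other than 5-HIAA, one between-arm test each gives about a 23–30% chance of at least one false significant result, and 15% if the outcomes are very strongly correlated. With the three non-echo outcomes also tested at 3 months, the range is about 29–39% for between-outcome correlations from 0.5 to 0. Within-arm testing raises the chance further and says nothing about the drug.

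These figures rest on assumed correlations, on my reading of how many tests the mixed models produce, and on each test holding its nominal 5% (both strains and TAPSE are analysed as categories, where the actual rate may be lower). Setting 5-HIAA aside is a judgement, since section 4.1 cites urinary levels and this trial measures plasma. No estimate, sample size or primary decision changes. The matter is worth correcting because the rule is explicit and the correction is cheap.

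**What to change.** Replace the closing rule in section 11.2 with:

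> Statistical significance (two-sided 0.05) is claimed only for one pre-named primary analysis: the between-arm comparison of 6-month percent change in NT-proBNP, by one stated model in the modified intention-to-treat set. Secondary between-arm differences are reported with 95% CIs; their p-values, all within-arm p-values, all 3-month p-values and all per-protocol p-values are nominal and support no claim of benefit. 5-HIAA is reported as a pharmacodynamic check.

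The team must fill in the stated model. Section 11.2 now offers both a t-test and a regression adjusted for the stratification factors, in two analysis sets, without saying which one decides.

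Only if a secondary claim is wanted, add Holm's procedure across the seven other 6-month contrasts (first step 0.05/7 = 0.0071) and adjust the first sentence of the replacement text to match. Holm holds the secondary family at 5%. Unless it is made conditional on a significant primary, the primary and secondary families together could reach 10% (5% + 5%).

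The change should be made before unblinding. It costs a few lines of text, needs no patients or data, and leaves the primary's power as it is. The downside is that fewer results may be called significant.
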